Clinical study protocol

Project title: Secreted heat shock protein 90 is involved in the pathogenesis of diabetic peripheral vascular disease

Scheme version/date: v1.0/2020-7-20

Research Department/Principal investigator: Department of Endocrinology and Metabolism/[name]

Sponsor/Address: Nanfang Hospital, Southern Medical University/[name]

Confidentiality Statement:

The information contained in this study protocol is provided for review only by the project investigator, the ethics committee, and relevant agencies. The copyright is owned by Nanfang Hospital of Southern Medical University. Without the approval of Nanfang Hospital of Southern Medical University, it is strictly prohibited to disclose any information to third parties unrelated to this study.

Summary of Research Scheme

Package name	The role of secretory heat shock protein 90 in the pathogenesis of diabetic peripheral vascular disease
Bidding for the unit	Nanfang Hospital, Southern Medical University
Principal investigator	[name]
Research center and responsible person	[name], Nanfang Hospital, Southern Medical University
The research object	II with type 1 diabetes
Research purpose	
Main purpose: II with type 1 diabetes, vascular lesion severity, and the relationship between heat shock protein 90 in serum.
 
Secondary purpose: serum heat shock protein 90 (HSP90) can predict the degree of vascular disease in diabetic patients.

The research group	The diabetic group had no PAD, had PAD, and had diabetic foot disease
Study design	According to the degree of peripheral artery disease, the patients were divided into three groups, and the content of heat shock protein 90 in serum of the patients was detected. To analyze the correlation between the degree of peripheral arterial disease and the content of heat shock protein 90 in serum.
The time limit	The 2020-9-1-2020-9-1
Sample size	150 cases, 50 cases in each group.
The inclusion criteria	
 Diagnostic criteria for diabetes: using WHO1999 diabetes diagnostic criteria, that is, (1) having diabetes symptoms (polyuria, polydipsia, and unexplained weight loss), and random (any time after meal) plasma glucose $\geq 11.1 \text{ mmol/L}$ (200 mg/dL); (2), or fasting (fasting for at least 8 hours) plasma glucose $\geq 7.0 \text{ mmol/L}$ (126 mg/dL); (3), or OGTT 2 hours plasma glucose $\geq 11.1 \text{ mmol/L}$ (200 mg/dL) Inclusion criteria of the diabetes PAD group: patients diagnosed as T2DM according to the above-mentioned diagnostic criteria for diabetes, and with (1) symptoms and signs of atherosclerotic occlusion (intermittent claudication, resting pain, reduced or absent pulsation

	
of dorsal foot artery, etc.); (2) Ankle-brachial arterial pressure index (ABI) ≤ 0.9; Toe brachial artery pressure index (TBI) ≤ 0.70; There was no three-phase pulse pattern of foot artery. Transcutaneous partial oxygen pressure (TcPO₂) $< 30 \text{ mmHg}$; (3) Evidence of atherosclerosis, atherosclerotic plaques, arterial stenosis or obstruction in carotid and/or lower extremity major arteries found by vascular color Doppler ultrasound.
 
3. Inclusion criteria for the diabetic foot group caused by PAD: the presence of infection, ulcer and/or deep tissue destruction of the foot was confirmed according to the above diagnostic criteria of diabetic PAD.
 
4. Agree to participate in the study and data collection, and sign the informed consent.

Exclusion criteria	
1. Diabetic ketoacidosis or hyperosmolar state occurs within 30 days;
 
Diabetic coma in 2 or 3 months, or severe hypoglycemia in nearly 1 month;
 
3. Diseases of tumor, immune system and hematopoietic system;
 
4. Other types of diabetes
 
5. Less than 40 years old

Validity analysis	The main observation indexes: II with type 1 diabetes, serum content of heat shock protein 90.
Statistical analysis	
Sample size determination:
 $n = \varphi^2 \left(\sum s_i^2 / g \right) / \left[\sum (\bar{X}_i - \bar{X})^2 / (g - 1) \right]$ 
Statistical analysis: SAS 9.2 statistical analysis software will be used for statistical analysis.

follow-up	No follow-up
Statistical method	Analysis of variance
schedule	
2020-9-1 -- 2020-10-10 Collect all samples
 
2020-10-10 -- 2020-10-15 Complete all sample tests
 
2020-10-15 -- 2020-10-20 Statistical analysis was completed

List of abbreviations and definitions of terms

Arterial lesions around PAD

OGTT oral glucose tolerance test

1. Research background

Diabetic foot disease is one of the most serious complications of diabetes, which brings great pain and economic burden to patients, with a global incidence of about 6%. In China, the incidence rate is 8.1%, and the amputation rate is 7.3%. Every year, more than 1 million diabetic patients have amputations, ranking first among non-traumatic amputations. According to the American Diabetes Association (ADA), the incidence of Peripheral Arterial Disease (PAD) in diabetic patients is twice that of non-diabetic patients, and the resulting lower limb ischemia is the main cause of the high mortality and disability rate of diabetic foot. According to the International Working Group on Diabetic Foot (IWGDF), about 50% patients with diabetic foot disease are complicated with PAD, and the degree of vascular stenosis is closely related to the prognosis. Severe limb ischemia is a higher cause of diabetic foot ulcer in China than in western countries. The main pathological change of diabetic PAD is atherosclerosis, and endothelial injury is the initial link of atherosclerosis. Oxidative stress is the central link in the mechanism of endothelial injury in diabetic vascular disease, and it is also the basis for us to model endothelial cells with high glucose and hydrogen peroxide.

Heat Shock Protein 90 (Hsp90) is an important type of Heat stress Protein. The molecular size of Hsp90 is 90-kDa. In eukaryotic cells, there are mainly two subtypes, α and β , and the content of Hsp90 accounts for 2–3% of the total Protein in cells. Involves in the correct folding and activation of intracellular proteins. Although Hsp90 is primarily involved in intracellular protective mechanisms, they can also be exposed to the plasma membrane and released in the extracellular space, resulting in detectable levels of Hsp90 in the blood. Extracellular heat shock proteins are involved in cell-cell

communication as well as immune and inflammatory processes. Hsp90 promotes cell survival, migration, inflammation and angiogenesis, and is therefore considered a promising target for cancer therapy. This led to the development of specific HSP90 inhibitors. More recently, these inhibitors have also been tested in diabetic animals. The use of the HSP90 inhibitor 17-DMAG significantly reduced atherosclerotic lesions and induced a more stable plaque phenotype in a mouse model with hyperglycemia and hyperlipidemia. Hsp90 is upregulated in human carotid atherosclerotic plaques (especially in unstable areas of plaques) and in patients' serums, triggering autoimmune antibodies against Hsp90 in patients.

2. Research Objectives

Main purpose: 2.1 **I** with type 1 diabetes, vascular lesion severity, and the relationship between heat shock protein 90 in serum.

2.2 Secondary purpose: serum heat shock protein 90 was used to predict the degree of vascular disease in diabetic patients.

3. Study endpoint

3.1 Primary end point: Patients were screened for diabetic angiopathy during hospitalization.

4. Study design

This study is a prospective study. It is planned to enroll 150 subjects, with 50 subjects in each group.

Subjects will not be given or offered any randomization or any study regimen-driven treatment during the study. If it is clinically applicable, treatment decisions and treatment options are made at the discretion of the treating physician.

5. Subjects

The subjects of this study is **I** crowd with type 1 diabetes.

Diagnostic criteria: 5.1 reference WHO1999 years diabetes diagnosis standard, specification and so on carries on the diagnosis of **I with type 1 diabetes.**

5.2 Inclusion criteria:

- Voluntarily signed informed consent;
- Over 40 years of age, regardless of gender

WHO1999 year after the diagnosis of diabetes guidelines, specifications Ⅱ

diagnosed with type 1 diabetes

5.3 Exclusion criteria:

- Diabetic ketoacidosis or hyperosmolar state occurs within 30 days;
- Diabetic coma in 3 months, or severe hypoglycemia in nearly 1 month;
- Diseases of tumor, immune system and hematopoietic system;
- Other types of diabetes
- The researcher judged that it was not suitable to participate in this study.

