11.2 Statistical methods

The analysis included baseline analysis and analysis of the relationship between the degree of vascular disease and serum HSP90.

11.3 Statistical Software and General Requirements:

- All statistical analyses were performed using SAS9.2 (or higher).
- The measurement data were described as mean, standard deviation and group number.

12. Research management

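### The synopsis plans a correlation between degree of PAD and serum HSP90, but degree is fixed at 50:50:50, so the size of any coefficient depends partly on the quotas and does not estimate the strength of the relationship in diabetic patients.

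*Protocol*

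**What the plan says.** In the Summary of Research Scheme, the Study design row forms the exposure variable from groups ("According to the degree of peripheral artery disease, the patients were divided into three groups") and then states the analysis: "To analyze the correlation between the degree of peripheral arterial disease and the content of heat shock protein 90 in serum". The groups are diabetes without PAD, diabetes with PAD, and diabetic foot disease. The Sample size row fixes their sizes ("150 cases, 50 cases in each group"), and section 4 repeats this: "It is planned to enroll 150 subjects, with 50 subjects in each group".

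The other statements on analysis are less specific. The Statistical method row reads "Analysis of variance", and section 11.2 promises an "analysis of the relationship between the degree of vascular disease and serum HSP90" without naming a measure. No correlation coefficient is named anywhere. No statement withdraws the correlation, reweights the groups, or limits how its size may be read.

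The aims concern diabetic patients in general. The secondary purpose in section 2.2, for example, reads: "serum heat shock protein 90 was used to predict the degree of vascular disease in diabetic patients". Section 1 gives diabetic foot disease as about 6% worldwide and 8.1% in China, and adds that "about 50% patients with diabetic foot disease are complicated with PAD".

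**The concern.** A correlation coefficient reflects the slope, the residual scatter and the spread of the explanatory variable. In this design one third of the sample sits at each level of degree because the quotas put it there. By the protocol's background figures, foot disease with PAD would be only about 3% to 4% of diabetic patients. The same HSP90 levels in the same kinds of patient would give a different coefficient under different quotas.

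The main purpose asks how vascular severity relates to serum HSP90. If the answer is reported as the size of r, or of variance explained, readers are likely to take it as the strength of that relationship among diabetic patients. This sampling does not estimate that quantity. The point concerns the measure used for the main purpose. It does not concern the validity of the hypothesis test.

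**Working it through.** **The plan's own figure.** Section 11.1 gives 50 per group, and the synopsis gives a formula for comparing several means. The figure cannot be reproduced because alpha, power, group means and SDs are not stated. Back-solving a one-way ANOVA with three groups of 50 and an assumed alpha of 0.05 gives Cohen's f = 0.256 at 80% power and 0.293 at 90%. For equally spaced means with step d (in within-group SDs), f = d × √(2/3). So d = 0.256/0.816 = 0.31, or 0.293/0.816 = 0.36. Steps of 0.3 to 0.5 SD are therefore a reasonable range to examine.

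**Inputs.**
- Quota mix: 1/3, 1/3, 1/3 (synopsis; section 4).
- Foot disease with PAD: 0.06 × 0.5 = 0.030 to 0.081 × 0.5 = 0.0405 (section 1). The protocol calls 6% and 8.1% incidence; using them as shares is an assumption.
- PAD without foot disease: not in the protocol; 20% and 46% assumed.
- Degree scored 0, 1, 2 and within-group SD of HSP90 set to 1: assumptions.

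**Formula, linear trend.** With v the variance of the score, r = d√v / √(d²v + 1).

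**Score variance.**
- Equal thirds: v = (0 + 1 + 4)/3 − 1² = 0.667.
- 76/20/4%: v = (0.20 + 0.16) − 0.28² = 0.282.
- 50/46/4%: v = (0.46 + 0.16) − 0.54² = 0.328.

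**Results, linear trend.**

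| Mix | v | r at d = 0.5 | r² at d = 0.5 | r at d = 0.3 |
|---|---|---|---|---|
| 50:50:50 quota | 0.667 | 0.378 | 14.3% | 0.238 |
| 76/20/4% | 0.282 | 0.256 | 6.6% | 0.157 |
| 50/46/4% | 0.328 | 0.275 | 7.6% | 0.169 |

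Over a wider set of assumed mixes (PAD without foot disease 10% to 50%, foot disease 3% to 8.1%), r at d = 0.5 runs from 0.22 to 0.31. The quota value is about 1.2 to 1.8 times as large. Spearman's rho, checked by simulation, behaves in the same way.

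**Where the inflation fails.** For general group means μ, r = cov(score, μ) / √(v × (1 + var μ)).
- *Plateau* (PAD and foot groups both 1 SD above no PAD). Quota: 0.333/√(0.667 × 1.222) = 0.37. 76/20/4%: 0.213/√(0.282 × 1.182) = 0.37. 50/46/4%: 0.270/√(0.328 × 1.25) = 0.42. Across the wider mixes the range is 0.30 to 0.43, so the quota value lies inside it.
- *Inpatient-type mix* of 40/30/30% (hypothetical): v = 1.5 − 0.9² = 0.69. At d = 0.5, r = 0.384 against 0.378 under the quota, which is almost equal and slightly higher.
- *Rise in the foot group only* (1 SD): 0.37 under the quota against 0.08 to 0.23 in the wider mixes, so here the inflation is larger.

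**What does not move.** With no HSP90 difference between groups, r = 0 under every mix, so the test of no association is sound. Group means and their differences do not contain v at all.

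**The case against.** The strongest reply is that the protocol does not commit to a coefficient. The word appears in one synopsis sentence of an evidently translated text, where it may mean no more than association. The named method is ANOVA and the sample-size formula is for several means. Section 11.2 speaks only of a relationship, and section 11.3 describes measurements by mean and SD. ANOVA is valid under quota sampling, and the choice of effect summary is often left to the statistical analysis plan.

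Much of this stands. It rules out saying that a coefficient is certain to be the headline result. It does not remove the point, because the protocol states a correlation and a quota in the same table and nothing withdraws or qualifies the first. Variance explained from the ANOVA would also depend on the quotas. The point rests on what the protocol states, and not on detail it leaves open.

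A reader might infer two stronger things. One is that the design sets the coefficient. It does not: at the same quota r is 0.24 for a 0.3 SD step and 0.38 for a 0.5 SD step. The other is that the coefficient must overstate the relationship. The documents do not support that either. PAD prevalence is not given and the pattern of HSP90 across groups is unknown. Section 3.1 also places screening during hospitalization, so an inpatient source mix is plausible.

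**Conclusion.** The point holds in a limited form. The size of any correlation coefficient, or of variance explained, depends partly on the 1:1:1 quotas and does not estimate the strength of the relationship in diabetic patients. Under a roughly linear trend and a community-like mix, r would be inflated by about 1.2 to 1.8 times. In the two example mixes at a 0.5 SD step, variance explained is about doubled (14.3% against 6.6% and 7.6%). These sizes rest on assumed PAD shares, on incidence figures used as shares, and on scores of 0, 1, 2. The direction is not assured, given the plateau and inpatient-type cases. The test of no association, the group means and the ANOVA are unaffected. The change is worth making because it is cheap and bears on how the main purpose is answered.

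**What to change.** In the synopsis Study design row, replace correlation as the measure of the main relationship with a comparison of serum HSP90 between the three groups. In section 11.2, specify HSP90 differences (or ratios) between groups with 95% confidence intervals from the ANOVA already planned, with a trend test across the ordered groups if wanted. If a correlation is still reported, use it only as a test of association. State that its size is conditional on the 1:1:1 sampling and is not the correlation in diabetic patients.

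The cost is a few lines of text and slightly more reporting from the same data and model. The headline may look less impressive than a single coefficient.

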6.3 Data source/data collection process

Data from this study were obtained by extracting routine clinical records of enrolled subjects. The investigator was required to complete the study's electronic case report form (eCRF) and/or record form based on the information entered in the patient's medical record throughout the monitoring period.

6.4 Data collection steps:

6.4.1 screening period

- (1) Signed Informed Consent
- (2) Complete inclusion and exclusion criteria verification
- (3) Medical history and demographic data were obtained
- (4) Laboratory tests: screening for diabetes-related complications, blood routine, CRP, coagulation function, renal function, etc

6.4.2 trial

- (1) Serum collection: the nurses collected the patients' fasting blood at 6:00 am in accordance with the routine blood collection procedures: 1 tube of procoagulant blood and 1 tube of anticoagulant blood were collected, each tube was no less than 3ml of blood;Store in a 4-degree

refrigerator for disposal.

(2) Collection of serum and plasma: the blood samples collected by the nurse were placed in a centrifuge, centrifuged at 3000 RPM for 15 minutes, and then the supernatant was collected.

(3) Laboratory test: the collected serum or plasma were quantitatively tested by HSP90 ELISA, and the results were analyzed. The remaining serum or plasma was stored in a negative 80 refrigerator.

6.4.3 follow-up

A telephone interview will be conducted every 3 months to assess the patient's prognosis (blood glucose and medication status, complication progression, PAD or diabetic foot disease).

7. Safety monitoring, reporting and medical treatment

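### The one inferential method named, analysis of variance, reads as one-way; for three non-randomised groups it cannot separate vascular severity from age or sex, and it does not use the group order

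*Protocol*

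**What the plan says.** In the Summary of Research Scheme the row for the statistical method reads only "Analysis of variance". The statistical analysis row of the same table gives a sizing formula built from the number of groups, the group SDs and the group means. Section 11.2 lists a baseline analysis and an analysis of how HSP90 relates to degree of vascular disease, and names no test, model or covariate.

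On the groups, the synopsis states: "According to the degree of peripheral artery disease, the patients were divided into three groups". They are no PAD, PAD and diabetic foot disease, 50 each. The planned analysis is described as follows: "To analyze the correlation between the degree of peripheral arterial disease and the content of heat shock protein 90 in serum". The foot group needs PAD and, in addition, that "the presence of infection, ulcer and/or deep tissue destruction of the foot was confirmed". Section 4 states: "Subjects will not be given or offered any randomization or any study regimen-driven treatment during the study". Section 5.2 admits patients "Over 40 years of age, regardless of gender". No matching or stratification is stated.

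At screening (section 6.4.1) "Medical history and demographic data were obtained", and renal function and CRP are measured. None of these is given a role in the analysis. The project title reads: "Secreted heat shock protein 90 is involved in the pathogenesis of diabetic peripheral vascular disease". The secondary purpose (section 2.2) is to predict degree of vascular disease from serum HSP90.

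**The concern.** Patients belong to these groups because of their disease, so the groups may also differ in age or sex. A one-way F test assigns the whole difference in mean HSP90 to group membership. The baseline analysis in section 11.2 can display an imbalance but does not adjust for it. Because the title is worded as a statement about pathogenesis, a significant F test that arose from an age or sex imbalance could be read as support for it.

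A second, smaller issue is order. The groups are ranked by severity and the stated aim is a correlation with that ranking, yet the omnibus F test gives the same result however the three groups are labelled. It can detect that the means differ but does not use the ranking.

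**Working it through.** **The plan's own figure.** The 50 per group can be neither reproduced nor refuted, because the protocol gives the formula and the result but not alpha, power, means or SDs. With alpha 0.05 assumed, 50 per group gives 80% power for equally spaced means about 0.31 SD apart.

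**Inputs.** From the protocol: 3 groups, 50 per group. Assumed: two-sided alpha 0.05; within-group SD of HSP90 equal to 1; a normal covariate with within-group SD 1, within-group correlation ρ with HSP90, and a mean shift of D SD between the extreme groups, equally spaced.

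**Step 1: unadjusted F test, no true severity effect.** The covariate alone produces group means (0, ρD/2, ρD). The noncentrality is

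λ = n Σ(μᵢ − μ̄)²/σ² = 50 × 2 × (ρD/2)² = 25(ρD)²,

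referred to F(2, 147) with critical value 3.058. At the extremes, ρ = 0.1 and D = 0.25 give λ = 25 × 0.025² = 0.016; ρ = 0.5 and D = 1.5 give λ = 25 × 0.75² = 14.06. Rejection rates:

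| D | ρ = 0.1 | ρ = 0.3 | ρ = 0.5 |
|---|---|---|---|
| 0.25 | 5.1% | 6.0% | 8.0% |
| 0.5 | 5.5% | 9.4% | 18.1% |
| 1.0 | 6.9% | 24.5% | 59.3% |
| 1.5 | 9.4% | 50.0% | 92.4% |

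ANCOVA on the same covariate rejects in about 5% in simulation (for example 5.0% at ρ = 0.3, D = 1.0 and 4.8% at ρ = 0.5, D = 1.5).

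**Step 2: order.** For equally spaced means (0, 0.315, 0.63), the F test has λ = 50 × 2 × 0.315² = 9.92 on 2 df: power 80.4%. The contrast (−1, 0, 1) has λ = 0.63²/(2/50) = 9.92 on 1 df: power 87.9%. Relabelling shows what the F test ignores: means (0, 0.25, 0.50) and (0.25, 0.50, 0) both give the F test 59.3%, while the contrast gives 70.0% and 23.7%. The contrast does not establish a gradient by itself either: with means (0, 0, 0.6) or (0, 1.0, 0.6) it is significant in about 85%.

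**Step 3: price of adjusting for two covariates.** Take true means (0, 0.315, 0.63) and two independent covariates, both shifted by D but unrelated to HSP90. Approximately, the variance of the adjusted extreme difference is 2/50 + 2D²/147, and λ = 0.63² divided by that variance, referred to F(2, 145):

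| D | variance | λ | power, formula | power, simulation |
|---|---|---|---|---|
| 0.5 | 0.0434 | 9.15 | 77% | 76% |
| 1.0 | 0.0536 | 7.40 | 67% | 66% |
| 1.5 | 0.0706 | 5.62 | 55% | 53% |

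The two agree to within about two points; the formula leaves out chance imbalance. These powers may be set against the unadjusted 80% only because the covariates are unrelated to HSP90. Where shifted covariates also correlate with HSP90, they move the unadjusted means as well. With three covariates at ρ = 0.3 each, the one-way test rejects in over 99.8% at shifts of 0.5 SD or more, so 80% is not the comparator there.

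**Step 4: precision.** The unadjusted 95% half-width of an adjacent difference is 1.976 × √(2/50) = 0.395 SD, so these differences will be imprecise in any case.

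**The case against.** The strongest objection is that this is detail for a statistical analysis plan. Analysis of variance as a family includes ANCOVA and linear contrasts, a plan not shown here may specify them, and sizing formulas are often simpler than the final model. This stands in part: the one-way reading is an inference, and a reader should not conclude that the protocol forbids adjustment. However, the protocol did not leave the method open. It named one, and an adjusted model using data already collected suits the stated design better.

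A reader might also infer that HSP90 comparisons in this study will be confounded. The documents do not support that: nothing in them says age or sex differ between the groups or relate to HSP90. The range from 5% to 92% reflects assumed inputs only.

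A third tempting reading is that the F test is invalid, or fails to test the relationship at all. It is a valid test of any difference, and a difference across severity groups is a relationship, which is how section 11.2 words the aim. Under a gradient it is only less efficient. An up-and-down pattern that would satisfy the F test and not a trend test is possible, but nothing in the protocol suggests one.

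Finally, it is tempting to put renal function into the main model. It may be a mediator as easily as a confounder, so adjusting for it could remove part of the association of interest. The same applies to CRP. For the prediction purpose, an unadjusted association is useful in its own right.

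**Conclusion.** The point holds in a limited form. The only inferential method named reads most naturally as one-way, and for three non-randomised groups it cannot separate vascular severity from age or sex. Whether that matters in this study is unknown. With mild imbalance (0.25 SD between extreme groups) the false-rejection rate stays at 5% to 8%; with 1.5 SD it runs from 9% to 92% for correlations of 0.1 to 0.5, against about 5% after adjustment. All of these figures rest on assumed inputs: alpha 0.05, unit SD, one normal covariate and an equally spaced shift. Ignoring order is an efficiency loss (about 80% against 88% power under an equally spaced gradient) and not an error. The change should be made, but it does not make the planned F test wrong.

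**What to change.** - Keep the one-way ANOVA as the unadjusted analysis; it remains useful for the prediction purpose.
- Before the data are seen, name a linear model (ANCOVA) of HSP90 on the three-level group with age and sex as covariates. Report the no-PAD vs PAD and PAD vs foot-disease differences with 95% CIs. Base any statement about vascular severity or pathogenesis on this model.
- For the stated correlation with degree of PAD, add a linear-trend contrast from the same model, read beside the two adjacent differences.
- Add renal function and CRP as covariates in sensitivity analyses only, since each may be a confounder or a mediator. Adding CRP does not remove the overlap between infection and membership of the foot group.

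Cost: wording, some extra analysis and two of 147 residual degrees of freedom; no new patients, samples or tests. If both covariates are imbalanced yet unrelated to HSP90, power of the adjusted group test falls from 80% to about 76%, 66% or 53% at shifts of 0.5, 1.0 or 1.5 SD (assumed inputs), with the sample size unchanged. Residual confounding remains possible after adjustment and should be stated in the report.
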